## 7.4. Screening

Eligibility against the inclusion and exclusion criteria will be checked by a delegated member of the research team. This will include assessment of functional impairment using the ECOG Performance Status Scale.

## 7.5. Study assessments

Appendix 1 (Section 13.1) shows the schedule of procedures.

The study team will prioritise assessments asking participants to complete as many as they feel able to at that visit, with the option of completion at a further visit, or of postal/ email/ online return for those parts of the assessment not requiring face to face input. Where possible, additional support with completing questionnaires e.g. for visually impaired, English is not first language, will be offered to maximise diversity, and reduce participation barriers where necessary.

#### **PAINSTORM Dundee Questionnaire**

A web-based version of the PAINSTORM Dundee questionnaire will be developed by Health Informatic Services (HIC), University of Dundee, this will be based on a modification of the previously used DOLORisk questionnaire (see Pascal et al 2019) and include:

**Demographics:** Age, gender, weight, height, years in education and working status, SIMD.

## **Past Medical History**

Co-morbidities (past and present)

- Concomitant medication
- Family History
- Cancer
- Details of cancer type and stage
- Oncological treatment including planned chemo protocol (and any changes to this with reasons)

## Characterisation of pain:

- EORTC-CIPN20
- BPI (including interference subscale).

## Intensity of the pain:

- Chronic Pain Grade
- BPI (intensity subscale)

## **Neuropathic descriptors:**

- DN4 questions
- NeuP Symptom Inventory

#### Pain location:

- List of body sites
- Body map

## Psychological and psychosocial:

- PROMIS (includes depression, anxiety, sleep, support
- Trauma questionnaire.
- MDASI
- IDS-SR
- EQ-5D-5L21
- Pain Catastrophizing Scale
- SOM-7
- TIPI

## Lifestyle:

- Smoking
- Alcohol
- Saltin-Grimby Physical Activity Level Scale
- Grooved pegboard test
- Step count (ActivPALTM accelerometer)
- Patterns of daily living (time spent sitting, standing, stepping and lying) using ActivPAL™ accelerometer.

#### Clinical examination

- NCI-CTCv5. (sensory and motor).
- QST: this is a measure of sensory perception in response to defined sensory stimuli. QST is performed according to a modification of the previously published protocol of the German Research Network on NeuP and is harmonised across the PAINSTORM consortium. We have previous experience of using QST in a similar patient population (Scott, Colvin et al 2012). There will be an option for a reduced QST protocol to assess mechanical (touch, pressure) and thermal sensation (warm/ hot; cool/ cold) if individual participants do not wish to undergo the more comprehensive assessment.
- TNSc is used for chemotherapy-induced neuropathy.
- The spatial extent of sensory deficits and sensory hypersensitivity will be recorded on a body map.

### **Blood samples:**

## Visit 1 - approx. 30ml

- Serum for neurofilament light chain and other potential biomarkers analyses
- Whole blood for storage for genetic analysis

## Visits 2 & 3 - approx. 20 ml

Serum for neurofilament light chain and other potential biomarkers analyses

Samples will be collected, processed and stored for future research. They will be stored by the Tayside Biorepository, with a portion of the serum being transferred to Imperial College London for planned biomarker analysis.

#### **MRI: Magnetic Resonance Imaging**

PAINSTORM Dundee CIPN Study has funding for a total of 200 scans. Sequential, eligible patients will be offered the opportunity to participate in this optional part of the study. Within funding constraints each participant will be scanned at baseline (before starting chemotherapy), and again after completion of chemotherapy. The aim of the neuroimaging investigation is to

- i) identify brain structural and functional changes associated with development of CIPN
- ii) identify brain structural and functional measures from the baseline scans that predict later development of CIPN.

All scanning will be done at the CRIF, Ninewells Hospital, following SOPs:

- i) Participants will receive standard high resolution brain structure scans (T1, T2 and Flair) which will be used for both neuroimaging analyses. (15 min).
- ii) Functional neuroimaging will then be done during which QST (see below) stimuli are manually applied by an assistant in the scanner room (10 min). Participants then take part in a task which involves playing a game to maximise winning (10 min) During both periods, participants are able to see pictures on a screen during scanning and make decisions using button presses.
- iii) After this diffusion tensor imaging data will be acquired which takes about 10 min.
- iv) Finally resting state fMRI data will be acquired (10 min).

The total time for the scanning session is about 1 hour. The CRIF staff have extensive experience of care of participants in a scanning environment. When in the scanning room, participants will have access to a button, which they can press to immediately terminate the scanning session if they wish to.

Images will be reviewed by a radiologist for incidental findings reporting. If clinically significant abnormalities are reported then this will be discussed with the treating clinical team and the participant.

## **Wearable Technology**

ActivPal™ accelerometers to collate measures of physical function including step count, patterns of daily living (*time spent sitting, standing, stepping and lying*) will be offered to participants (optional). Participants will be asked to wear them in the week prior to the first cycle of chemotherapy, mid-way and at the end of their chemotherapy.

#### 7.6. Long term follow-up assessments

No long-term follow-up is planned, however, all participants consented will be asked if they wish to be contacted about future research.

#### 7.7. Withdrawal criteria

All participants are free to withdraw at any time and are not obliged to give reason(s). The PI or delegate will make a reasonable effort to ascertain the reason(s), both for those who express their right to withdraw and for those lost to follow up, while fully respecting the individual's rights. The investigator may withdraw a participant at any time if it is in the best interest of the participant.

If a participant withdraws, or is withdrawn, their data and any research tissue collected up to that point will be retained unless the participant expresses the wish to withdraw their data and/or tissue. Those withdrawn, including those lost to follow-up, will be identified and a descriptive analysis of provided, including the reasons for their loss, if known, and its relationship to treatment and outcome.

#### 7.8. Storage and analysis of clinical samples

Serum will be collected for neurofilament light chain and other potential biomarker analysis. A portion of this serum will be centrally stored within Tayside Biorepository on a short-term basis prior to being transferred to Imperial College London where biomarker analysis shall be completed. An accredited courier e.g., Marken will be used by the Biorepository to ensure safe frozen transport of samples.

Surplus blood (and serum) samples will be stored for future research use. Samples will be stored within appropriate secure, alarmed freezers within the research lab and samples will be registered with Tayside Biorepository. Alternatively, where there is capacity Tayside Biorepository will be used to store surplus study samples within their own freezers. Future use of surplus samples will be governed via the Tayside Tissue Access Committee to provide delegated ethical approval subject to the conditions of consent.

Excess biological samples originating from Tayside that are being taken for clinical reasons may be stored for future use if no longer required for clinical purposes. The research team will work with the biorepository and the appropriate clinical teams to ensure appropriate interception of these samples so that de-identification, processing and storage can be carried out in accordance with the Scottish Human Tissue Accreditation Scheme.

Surplus samples originating from Tayside participants that require biobanking will be pseudoanonymised. This will therefore allow the biorepository or associated research fellow to work with the Health Informatics Centre to associate data with the sample and securely transfer the data to a researcher for future use after receiving delegated ethics.

## 7.9. End of study

The end of study is defined as last participant, last visit. The Sponsor and/or PI have the right at any time to terminate the study for clinical or administrative reasons.

The end of the study will be reported to the Sponsor, REC and NHS R&D Office(s) within 90 days.

A clinical study report will be submitted to the Sponsor and REC within 1 year of the end of the study.

#### 8. STATISTICS AND DATA ANALYSIS

## 8.1. Sample size calculation

The sample size of n=200 will provide a robust, high- quality dataset of deeply phenotyped participants for use in PAINSTORM and beyond. The neuroimaging component will be one of the biggest to date in this patient population.

#### 8.2. Planned recruitment rate

We estimate that recruitment of 200 participants is expected to be completed within approximately 30 months (i.e. at a rate of ~ 2 participants per week). Pre-funding work with people with lived experience of undergoing chemotherapy, combined with known new patient numbers in Tayside Cancer Service indicate that this is a realistic target recruitment rate.

#### 8.3. Statistical analysis plan

A statistical analysis plan (SAP) will be prepared and finalized prior to database lock and final analysis.

#### 8.4. Participant population

The participant populations will be on an Intention-to-treat basis of participants with at least one round of chemotherapy. A complete cases analysis may be added for specific outcomes. This will be defined in the SAP.

#### 8.5. Statistical analysis of clinical data

For the primary analysis, participants will be classified as having a neuropathic or nonneuropathic component, based on their phenotype. Neuropathic phenotypes will be defined as a change of at least 2 on the sensory subscale of the EORTC-CIPN20 questionnaire and/ or dose reduction/ cessation of chemotherapy at any time during the chemotherapy. The primary analysis will be performed on the basis of these two groups. This definition may be modified as PAINSTORM Work package 2 evolves, which focuses on improving assessment to better reflect the experience of people living with NeuP(see 8.7). All continuous variables will be summarised using the following descriptive statistics: n (non-missing sample size), number of missing records, mean, standard deviation, median, maximum and minimum.

The frequency and percentages (based on the non-missing sample size) of observed levels will be reported for all categorical measures.

All summary tables will be structured with a column for NeuP group and an additional column for the total population relevant to that table/treatment, including any missing observations.

The primary analysis will examine the factors which predict the classification into the two groups and aim to establish a prediction model.

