#### 3. OBJECTIVES AND OUTCOME MEASURES/ENDPOINTS

#### 3.1. Hypothesis

An individual's risk of developing acute or chronic CIPN can be predicted by specific psychosocial, genetic and clinical risk factors.

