#### 3.5. Table of Endpoints and outcomes:

**Timepoints:** Face to face assessments at baseline, mid-chemotherapy, end of chemotherapy (timing depends on chemotherapy schedule), with all detailed measures. Note: Blood sampling MRI and use of physical activity monitor are optional (participant preference); MRI will be

offered to 100 eligible participants sequentially. Participants will complete a reduced questionnaire set prior to every cycle of chemotherapy. This can be completed remotely (paper/email/telephone/online) according to participant preference. Pain measures are only completed if pain is present.

Objectives	Outcome Measures	Timepoints measured
Primary		
Development (or persistence) of painless or painful CIPN	EORTC-CIPN20     Change in chemotherapy/dose reduction due to neurotoxicity.	Baseline, mid and end of chemotherapy 3, 6, 9 and 12 months after completion of chemotherapy.
	Pain location: List of body sites / Body map.	Baseline, mid and end of chemotherapy 3, 6, 9 and 12 months after completion of chemotherapy.
	Total Neuropathy Score clinical (TNSc)	Baseline, mid and end of chemotherapy.
Pain severity	
 
Chronic Pain Grade
 
Brief Pain Inventory (BPI) Numeric Rating Scale (average in last 24 hours)
 
	Baseline mid and end of chemotherapy at 3, 6, 9 and 12 months after completion of chemotherapy.
Secondary		
Lifestyle	
 
Eastern Cooperative Oncology Group (ECOG) Performance Status Scale
 
Any changes to planned oncological treatment
 
	
 
Baseline, mid and end of chemotherapy
 
Baseline, mid and end of chemotherapy
 

	Past medical History/ co-morbidities     Family History     Details of cancer type and stage     Oncological treatment including         planned chemo protocol (and any changes to this with reasons)     Duration of CIPN     Smoking questionnaire     Alcohol questionnaire     Illicit drugs	• Baseline
	Concomitant medication	Baseline, mid and end of chemotherapy at 3, 6, 9 and 12 months after

	
 
Physical function: Saltin-Grimby Physical Activity Level Scale
 
Step count (ActivPAL™ accelerometer)
 
Patterns of daily living (time spent sitting,
 
	
 
completion of chemotherapy.
 
Baseline, mid and end of chemotherapy at 3, 6, 9 and 12 months after completion of chemotherapy.
 
Baseline, mid and end of chemotherapy
 

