#### 6. PARTICIPANT ELIGIBILITY CRITERIA

#### 6.1. Inclusion criteria

18 years or older

- Planned course of potentially neurotoxic chemotherapy for the treatment of cancer. This
  includes the following:
  - Platinum drugs
  - Taxanes
  - Vinca alkaloids
  - Epothilones
  - Proteasome inhibitors
  - Thalidomide
  - Vedotin-based drugs
  - Checkpoint inhibitors

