#### 6.2. Exclusion criteria

- Incapacity to give consent or to complete the study questionnaires due to insufficient language command or mental deficiencies, in the opinion of the investigator.
- Functional impairment ECOG Performance Status Scale great than or equal to 3 at baseline.
- Concurrent clinically defined severe physical or psychiatric disorders that would preclude accurate phenotyping.
- Moderate to severe pain from other causes that may confound assessment or reporting of pain if unable to differentiate from CIPN.
- Patients who are in the opinion of the investigator, or treating oncology team, unsuitable for participation in the study.

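### Section 8.5 sets no baseline condition, so a participant who enters with neuropathy and has a stable score and no dose change joins the non-neuropathic reference group

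*Protocol*

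**What the plan says.** **Who can enter.** Protocol 6.1 asks for age 18 or older and a "Planned course of potentially neurotoxic chemotherapy for the treatment of cancer". It does not ask for a first course or for absence of neuropathy. The nearest named exclusion in 6.2 is "Moderate to severe pain from other causes that may confound assessment or reporting of pain if unable to differentiate from CIPN". That concerns confounding pain, so painless or mild neuropathy passes it. The other exclusions that could apply are severe disorders that preclude phenotyping and the judgement of the investigator or oncology team.

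**Who is analysed.** Section 8.4 takes everyone with at least one round of chemotherapy.

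**How they are classified.** For the primary analysis, section 8.5 says that "participants will be classified as having a neuropathic or nonneuropathic component, based on their phenotype". It has two routes to being a case. The first is: "Neuropathic phenotypes will be defined as a change of at least 2 on the sensory subscale of the EORTC-CIPN20 questionnaire". The second, joined by and/or, is "dose reduction/ cessation of chemotherapy at any time during the chemotherapy". Everyone else is non-neuropathic. There is no absolute threshold, no baseline condition and no third group, and "The primary analysis will be performed on the basis of these two groups". The same section then sets out to model which factors predict group membership.

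**What is asked.** The hypothesis in 3.1 concerns the "risk of developing acute or chronic CIPN". The primary objective in 3.3 covers both development and maintenance of CIPN, painful or not. One aim of the imaging in 7.5 is to find baseline brain measures that predict later development.

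**The concern.** The comparison group for a question about developing CIPN should consist of people who could have developed it and did not. Under 8.5 it can also hold people who already had neuropathy at entry and did not change. They are outside the risk set for development. Where their neuropathy is CIPN that persists, they are cases for the maintenance half of the objective, and the non-neuropathic label is then plainly wrong.

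Characteristics that go with existing neuropathy, such as earlier neurotoxic treatment, abnormal baseline sensory testing or TNSc, raised serum markers or altered baseline imaging, would be over-represented in the reference group. Their association with becoming a case would be expected to shrink. These are among the predictors the study was set up to examine, and the resulting model would answer a mixture of two questions.

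**Working it through.** **1. Does the rule misfile anyone?** Take a participant with painless neuropathy from an earlier course who now starts another.
- 6.1: eligible.
- 6.2: not excluded by any named criterion, unless the disorder is severe enough to preclude phenotyping or the participant is judged unsuitable.
- 8.4: analysed after one round of chemotherapy.
- 8.5: sensory score changes by less than 2 and there is no dose reduction or cessation, so neither route is met.
- Result: non-neuropathic.

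Both conditions are needed. If the dose is reduced or chemotherapy is stopped, the same person becomes a case.

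**2. How large could this be?** The protocol gives no prevalence of neuropathy at entry. Section 8.1 states 200 participants without an event rate, effect size, significance level or power, so there is no planned figure to reproduce. What follows is illustration.

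Inputs:
- N = 200 (8.1).
- i = 0.67, share of the remaining participants who become cases (section 1 gives about 67% CIPN during chemotherapy).
- b = 0.05 to 0.20, share entering with neuropathy. *Assumed.*
- s = 0.5, share of those who keep a stable score and have no dose change. *Assumed.*

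Affected share of the reference group = b·s / [b·s + (1 − b)(1 − i)]

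| b | Stable, with neuropathy | Non-cases without baseline neuropathy | Affected share |
|---|---|---|---|
| 5% | 200 × 0.05 × 0.5 = 5 | 190 × 0.33 = 62.7 | 5/67.7 = 7.4% |
| 10% | 200 × 0.10 × 0.5 = 10 | 180 × 0.33 = 59.4 | 10/69.4 = 14.4% |
| 20% | 200 × 0.20 × 0.5 = 20 | 160 × 0.33 = 52.8 | 20/72.8 = 27.5% |

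The result depends on s. If those with baseline neuropathy become cases as often as the rest (s = 0.33), the shares are 5%, 10% and 20%. If none of them becomes a case (s = 1), they are 13.8%, 25.2% and 43.1%.

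**3. What would that do to an association?** Assume a factor present in 30% of true non-cases with a true odds ratio of 2.5. Its frequency in cases is 2.5 × 0.30 / (0.70 + 2.5 × 0.30) = 0.517. Assume also that stable participants with baseline neuropathy carry it as often as cases do. With affected share c, its frequency in the reference group is (1 − c) × 0.30 + c × 0.517. The observed odds ratio is the case odds, 0.517/0.483 = 1.071, divided by the reference odds.

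| b | c | Reference frequency | Observed odds ratio | Power, whole cohort (cases v reference) | Power, restricted (cases v reference) |
|---|---|---|---|---|---|
| 5% | 7.4% | 0.316 | 2.32 | 78% (132.3 v 67.7) | 82% (127.3 v 62.7) |
| 10% | 14.4% | 0.331 | 2.16 | 72% (130.6 v 69.4) | 80% (120.6 v 59.4) |
| 20% | 27.5% | 0.360 | 1.91 | 58% (127.2 v 72.8) | 75% (107.2 v 52.8) |

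Power is for a two-sided 5% comparison of two proportions (assumed): Φ[(|p1 − p2| − 1.96·SE0)/SE1], with SE0 from the pooled proportion and SE1 from the separate ones. With no one affected and 134 v 66, it is 84%. The restricted column drops everyone with baseline neuropathy, so the odds ratio stays at 2.5. Under these assumptions the smaller, cleaner comparison has more power than the larger, mixed one.

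**The case against.** The strongest reply is that a change score is the right tool for CIPN caused by this course of chemotherapy. Someone whose earlier neuropathy is unchanged has not developed CIPN from it, so calling that person a non-developer is not an error of case status. A model for everyone starting chemotherapy, with baseline status as a predictor, is a legitimate reading of 3.1. Section 8.3 leaves detail to a SAP, baseline CIPN20 and TNSc are scheduled, and 8.5 lists no covariates, so adjustment or restriction remains open.

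Part of this stands. For development, the fault lies in the risk set and the label rather than in a wrong count of events. But 8.5 does more than stay silent: it fixes the two groups and bases the primary analysis on them. Its modification clause concerns Work package 2, whose findings 8.7 treats as exploratory, not baseline status. For maintenance the label remains wrong.

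Four stronger readings are tempting and are not supported:
- *That classification rests on change alone.* It does not, because dose reduction or cessation also makes a case. Section 1 notes that severe CIPN can force either, so some people with established neuropathy would be counted as cases.
- *That the protocol expects participants with CIPN at entry.* The table in 3.5 lists "Duration of CIPN" at baseline, but in a merged cell that also holds changes to the chemotherapy plan, which cannot be known before it starts. The item appears neither in the questionnaire content of 7.5 nor as a row in Appendix 1. It is weak evidence.
- *That associations could be reversed.* The calculation shows dilution only, and that under an assumed exposure pattern.
- *That up to 30% of the reference group is affected.* Dividing 20 by a fixed reference group of 66 gives 30%, but the reference group itself changes with b and s. The consistent figure is about 27%.

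**Conclusion.** The point holds in limited form. Nothing named in 6.1 or 6.2 keeps out painless or mild pre-existing neuropathy, and the primary rule in 8.5 places such a participant in the reference group when the score is stable and the dose unchanged. That follows from the text and needs no assumption.

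The size does. The share entering with neuropathy (5-20%) and the half who stay stable without dose change are both assumed, and investigator discretion may remove some of these people before entry. On those inputs about 7-27% of the reference group is affected. The drop in odds ratio from 2.5 to between 2.32 and 1.91 rests further on the assumed exposure pattern. Dilution is the expected direction, and its amount is unknown until baseline data are seen. The point should be settled before the classification is used.

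**What to change.** In 8.5, and correspondingly in the SAP:
- Define baseline neuropathy in advance, with a stated cut-off, from the baseline CIPN20 sensory score, TNSc and medical history.
- Fit the development model in participants free of it.
- Report those with baseline neuropathy separately as worsening or persistence, descriptively if they are few.
- Include the baseline CIPN20 sensory score as a covariate in any whole-cohort model. That model can be kept alongside the restricted one.

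The cost is wording in the protocol and SAP. All the data are already scheduled at baseline, and eligibility need not change. The development model loses the participants with baseline neuropathy, 200 × 0.05 to 0.20 = 10 to 40 under the assumption, and the separate group of that size would support little modelling of its own.

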#### 3.3. Primary objective

Use of a deep phenotyping approach to identify psychosocial, clinical and neurobiological factors that are associated with the development and/ or maintenance of painful or non-painful CIPN, as a result of neurotoxic chemotherapy for cancer.

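### Section 8.5 counts any dose reduction or cessation as neuropathic, while section 3.5 counts only changes due to neurotoxicity, so stops for other reasons become false CIPN cases

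*Protocol*

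**What the plan says.** Section 8.5 gives the operative rule for the primary analysis. Its first limb is the questionnaire: "Neuropathic phenotypes will be defined as a change of at least 2 on the sensory subscale of the EORTC-CIPN20 questionnaire and/ or". The second limb follows directly: "dose reduction/ cessation of chemotherapy at any time during the chemotherapy". Because the limbs are joined by and/or, either is sufficient alone. The resulting groups are the outcome of the main model: "The primary analysis will examine the factors which predict the classification into the two groups and aim to establish a prediction model".

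Section 3.5 lists the treatment component among the primary outcome measures with a cause attached: "Change in chemotherapy/dose reduction due to neurotoxicity". Lower in the same table, under the secondary lifestyle measures, it lists an all-cause item: "Any changes to planned oncological treatment".

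The primary objective in section 3.3 concerns "painful or non-painful CIPN, as a result of neurotoxic chemotherapy for cancer". The questionnaire content in section 7.5, under Past Medical History, includes the "planned chemo protocol (and any changes to this with reasons".

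**The concern.** The endpoint table and the analysis section define the same primary component differently, and the analysis section is the one that would be programmed. It drops the attribution to neurotoxicity. A participant with an unchanged CIPN20 score whose treatment is reduced or stopped because of progression, low blood counts, infection or choice then enters the model as a CIPN case.

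This could do more than add noise. Age, performance status, comorbidity and cancer stage are all collected at baseline and are natural candidate predictors. If they also drive dose reduction in general, the model will present predictors of poor chemotherapy tolerance as predictors of CIPN. Recruiting more participants would not remove that bias. If CIPN is as common as the background section suggests, the rule also takes people out of the smaller, non-neuropathic group, which limits how many predictors the model can support.

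There is a lesser mismatch of terms: 3.5 speaks of a change in chemotherapy or dose reduction, 8.5 of dose reduction or cessation.

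**Working it through.** **Text comparison**

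| Point | Section 3.5, primary | Section 8.5 |
|---|---|---|
| Event | change in chemotherapy, dose reduction | dose reduction, cessation |
| Cause | neurotoxicity | none stated |
| Sufficient alone? | not stated | yes (and/or) |

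No other section adds the cause to the 8.5 rule. Section 8.5 allows its definition to be modified, but only as Work package 2 evolves, and section 8.7 makes findings from that package exploratory. Neither route deals with attribution. Section 3.5 lists all-cause changes separately as secondary, so the protocol itself treats the two as different measures.

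**Size.** The protocol states no figure to reproduce here: section 8.1 gives n=200 without an event rate, effect size or power. The following is illustration.

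Inputs:
- N = 200 (section 8.1).
- p = share with true CIPN. Section 1 gives about 67% during chemotherapy and about 33% long term. These are background frequencies, not the share meeting the 8.5 rule.
- q = share of participants without CIPN who have a reduction or stop for another reason. The protocol gives no value; the range is assumed.

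False cases = N × (1 − p) × q. People who also meet the CIPN20 limb are not false cases, and the formula already leaves them out.

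At p = 0.67 there are 200 × 0.67 = 134 true cases and 66 non-cases.
- q = 10%: 66 × 0.10 = 6.6 false cases; 6.6 / 140.6 = 4.7% of the neuropathic group; 59.4 remain in the reference group.
- q = 40%: 66 × 0.40 = 26.4 false cases; 26.4 / 160.4 = 16.5%; 39.6 remain.
- At q = 5% the count is 3.3 (2.4%).

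At p = 0.33, q from 5% to 40% gives 6.7 to 53.6 false cases, or 9% to 45% of those classed neuropathic.

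**A spurious predictor.** Take a factor with no effect on CIPN that raises q from 10% to 30% (a hypothetical contrast).
- p = 0.67: with the factor, 0.67 + 0.33 × 0.30 = 0.769, odds 0.769 / 0.231 = 3.33. Without it, 0.67 + 0.33 × 0.10 = 0.703, odds 0.703 / 0.297 = 2.37. Apparent OR = 1.41.
- p = 0.50: (0.65 / 0.35) / (0.55 / 0.45) = 1.52.

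**A true predictor, error unrelated to it.** Assume a binary factor split 100/100, a true OR of 2, and q the same in both halves, over q = 5% to 40%.
- p = 0.67: the observed OR is 1.97 to 1.79, and power falls from 0.63 to between 0.59 and 0.36.
- p = 0.33: the observed OR is 1.87 to 1.46.

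**The case against.** The best defence is that 8.5 is shorthand. It is defining neuropathic phenotypes, the objective concerns CIPN caused by chemotherapy, and 3.5 shows what was intended. A statistical analysis plan is due before database lock (section 8.3) and could spell out the attribution. That recovers the likely intention but does not make the operative rule correct: the author of that plan would have two incompatible definitions of the primary outcome, one of them explicit and broader, and would choose between them after data had been collected.

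Other points stand as limits on the finding:
- No passage shows that the error is differential. It is a plausible risk, and excluding ECOG 3 or above at baseline (section 6.2) narrows one of the likely drivers.
- If the error is unrelated to the predictors and CIPN is common, attenuation is modest.
- Every other-cause rate used here is assumed, and the non-neuropathic group is the smaller one only if CIPN affects more than half.
- Cessation can be read as one kind of change in chemotherapy, so the difference in terms is loose wording more than a conflict.
- Collection of reasons during treatment is not explicit. In 3.5 the item with reasons sits in a block timed at baseline, and the Appendix 1 row for treatment alterations at every visit does not mention reasons.

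**Conclusion.** The concern holds. Sections 3.5 and 8.5 contradict each other on a component of the primary outcome, and 8.5 as written puts people without neuropathy into the neuropathic group. This is an error in a definition that the protocol fixes, and it does not depend on any assumed rate.

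The size does depend on assumptions. If 67% truly have CIPN and 10% to 40% of the rest have a reduction or stop for another reason, about 7 to 26 of 200 participants are misclassified. The consequence that matters most is an apparent association for a factor unrelated to CIPN, with an OR of 1.41 to 1.52 in the hypothetical contrast above. Because the outcome of the primary model is affected and the repair is small, it must be made before analysis.

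**What to change.** Reword the second limb of 8.5 to count dose reduction, cessation or change of chemotherapy recorded as due to neurotoxicity, and use the same wording in 3.5, which does not currently name cessation. Classify participants whose treatment changes for any other reason on CIPN20 alone. State in 3.5 and Appendix 1 that the reason for each change is recorded during treatment as well as at baseline, as a coded field. Report two sensitivity analyses: the all-cause version of the rule, and CIPN20 alone.

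The cost is one clause in 8.5, a matching edit in 3.5 and one coded field. If reasons are already being captured at each visit, no new data are needed. Attribution to neurotoxicity is a clinical judgement and will sometimes be uncertain; the two sensitivity analyses show how much depends on it. The change concerns only how participants are classified for analysis and affects no treatment decision.
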